## 5. ANALYSIS POPULATIONS

Prior to the locking of the database, agreement of subjects' assignment to each of the analysis populations and identification of major protocol deviations are to be determined in collaboration with Circassia at a blind data review (BDR) meeting. The authorisation of analysis sets is required prior to the final locking of the database and routine study unblinding.

The analysis populations below are described in detail in the latest version of the BDR plan, including the criteria to be used in defining each of these analysis populations.

### 5.1. ALL SUBJECTS ENROLLED [ENR] POPULATION

The Enrolled [ENR] population is to consist of all subjects that signed informed consent.

### 5.2. RANDOMISED [RND] POPULATION

The Randomised (RND) population is to consist of all subjects in the ENR population who passed both the Screening assessments and the BAE period and are subsequently randomised to study medication.

### 5.3. INTENT TO TREAT [ITT] POPULATION

The Intent to Treat (ITT) population is to consist of all subjects who are randomised, who have received at least one dose of study medication. Subjects are to be reported by the treatment they were randomised to. The ITT is the primary population for the study and all the primary and secondary efficacy analyses are to be based on the ITT population.

## 5.4. SAFETY [SAF] POPULATION

The Safety (SAF) population is to consist of all subjects that received at least one dose of study medication (HDM-SPIRE or placebo) and have at least one post-baseline safety assessment available. Subjects are to be reported by the treatment they actually received. The Safety population is to be used for all of the safety endpoints.

## 5.5. PER PROTOCOL [PP] POPULATION

The Per Protocol (PP) population is to consist of all subjects in the ITT population who have no major protocol deviations likely to affect the integrity of the study and who completed all study visits. Allocation of subjects to the PP population and all protocol deviations are to be fully documented in the BDR report. The PP population is to be evaluated for the primary variable to confirm results from the ITT population. Subjects are to be reported by the treatment they were randomised to.

# 6. GENERAL CONSIDERATIONS

## 6.1. REFERENCE START DATE AND STUDY DAY

Study Day is to be calculated from the reference start date, and is to be used to show start/stop day of assessments and events.

Reference start date is defined as the day of the first administration of study medication, (Day 1 is the day of the first administration of study medication), and is to appear in every listing where an assessment date or event date appears.

- If the date of the event is on or after the reference date then:

Study Day = (date of event – reference date) + 1.

- If the date of the event is prior to the reference date then:

Study Day = (date of event – reference date).

In the situation where the event date is partial or missing, Study Day, and any corresponding durations are to appear partial or missing in the listings.

## 6.2. BASELINE

For all safety variables, unless otherwise specified, Baseline is defined as the last non-missing measurement taken prior to reference start date (including unscheduled assessments or retests). In the case where the last non-missing measurement and the reference start date coincide, that measurement is to be considered pre-baseline, but AEs and medications commencing on the reference start date are to be considered post-baseline.

Document: TH005 SAP Version 2.docx  
Author: [name]

Version Number: 2.0  
Version Date: 24MAR2017

Template No: CS\_TP\_BS016 – Revision 3  
Effective Date: 01May2012

Reference: CS\_WI\_BS005

Copyright © 2012 Quintiles Transnational Corp. All rights reserved.  
The contents of this document are confidential and proprietary to Quintiles Transnational Corp. Unauthorized use, disclosure or reproduction is strictly prohibited.

---

For all efficacy variables Baseline is defined as the measurement taken during the BAE period prior to reference start date.

## 6.3. RETESTS, UNSCHEDULED VISITS AND EARLY TERMINATION DATA

In general, for by-visit summaries, data recorded at the nominal visit is to be presented. Unscheduled measurements are not to be included in by-visit summaries, but may contribute to the Baseline value.

In the case of a retest at any post Baseline visit (same visit number assigned but a different date and/or time of assessment), the first measurement (original value) for that visit is to be used for by-visit summaries.

Listings are to include scheduled, unscheduled, retest and early discontinuation data.

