## 6.4.4.4 Laboratory Assessments

Blood samples using the Vacutainer® system for haematology and biochemistry tests and urine samples for urine dipstick tests will be obtained at Screening (Visit 1B/C), at the End of Dosing Assessment (Visit 3I) and at the Period 3 Follow-Up (Visit 5).

Blood samples for Der p, Der f and perennial allergen specific IgE will be obtained at Screening (Visit 1A) and will be measured by ImmunoCAP®. At the End of Dosing Assessment (Visit 3I) and at Period 3 Follow-Up (Visit 5) blood samples for Der p and Der f specific IgE, measured by ImmunoCAP®, will be obtained.

A blood sample will be taken at screening only for measurement of a fixed panel of Der p allergens using an immune-affinity based analysis technology such as ImmunoCAP®.

Urine samples for pregnancy tests will be collected from FOCBP and analysed immediately at Screening (Visit 1B/C), before dosing at Study Medication Administration Visits (Visits 3A-3H), at the End of Dosing Assessment (Visit 3I) and at Period 3 Follow-Up (Visit 5).

The following parameters will be measured:

Haematology: haematocrit, haemoglobin, red blood cells, white blood cells (WBC),

WBC differentials (neutrophils, eosinophils, basophils, lymphocytes,

monocytes) and platelets.

Biochemistry: sodium, potassium, chloride, urea, creatinine, calcium, phosphorus,

total protein, albumin, uric acid, total bilirubin, glucose (random), lactate dehydrogenase, creatine phosphokinase, alanine transaminase, aspartate transaminase, gamma glutamyltransferase, and alkaline

phosphatase;

Blood samples will be collected for assay of tryptase in the case of a

suspected anaphylactic response [see Section 6.2.2]).

Urine dipstick: pH, protein, ketones, blood and glucose.

Immunology: Der p, Der f and relevant perennial allergen specific IgE (measured by

ImmunoCAP®).

Additional tests may be performed if clinically warranted. Abnormal values should be followed up they have returned to normal or an adequate explanation has been established.

All laboratory test reports must be reviewed, signed and dated by the Investigator or delegated physician. Reports will then be filed with the subject's medical record. The Investigator will comment on all abnormal results and determine whether it is clinically significant. These assessments will be recorded in the eCRF.

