#### 6.4.4.5 FEV1

The FEV1 will be measured at Screening (Visit 1B/C), prior to and 30 minutes after Study Medication Administration (Visits 3A-3H), at the End of Dosing Assessment (Visit 3I), and at the end of PAC1, PAC2 and PAC3 (Visits 4B, 4D and 4F). Asthmatic subjects should not use their asthma medication for a minimum of 4 hours prior to the spirometry assessment.

At each assessment FEV1 will be measured according to the American Thoracic Society guidelines with the subject sitting and the highest reading will be recorded in the eCRF.

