# APPENDIX 4 World Allergy Organization Subcutaneous Immunotherapy Systemic Reaction Grading System

Grade 1	Grade 2	Grade 3	Grade 4	Grade 5
Symptom(s)/sign(s) of one organ system presenti  Cutaneous  Generalized pruritus, urticaria, flushing or sensation of heat or warmthii or  Angioedema (not laryngeal, tongue or uvular) or  Upper respiratory  Rhinitis (e.g. sneezing, rhinorrhoea, nasal pruritus and/or nasal congestion)  or	Symptom(s)/sign(s) of more than one organ system present  or  Lower respiratory  Asthma: cough, wheezing, shortness of breath (e.g., less than 40% PEF or FEV1 drop, responding to an inhaled bronchodilator)  or	Lower respiratory  Asthma (e.g., 40% PEF or FEV1 drop, NOT responding to an inhaled bronchodilator)  or  Upper respiratory  Laryngeal, uvula or tongue oedema with or without stridor	Lower or Upper respiratory  Respiratory failure with or without loss of consciousness  or  Cardiovascular  Hypotension with or without loss of consciousness	Death
Throat-clearing (itchy throat)  or  Cough perceived to come from the upper airway, not the lung, larynx, or trachea  or  Conjunctival  Conjunctival erythema, pruritus or tearing  Other  Nausea, metallic taste, or headache	Gastrointestinal Abdominal cramps, vomiting, or diarrhoea or Other Uterine cramps			

Patients may also have a feeling of impending doom, especially in Grades 2, 3, or 4.

Note: children with anaphylaxis seldom convey a sense of impending doom and their behaviour changes may be a sign of anaphylaxis, e.g., becoming very quiet or irritable and cranky.

DATE 01 APRIL 2015 PROTOCOL IDENTIFIER: TH005

Scoring includes a suffix that denotes if and when epinephrine is or is not administered in relationship to symptom(s)/sign(s) of the systemic reaction: a, ≤5 minutes; b, >5 minutes to ≤10 minutes; c, >10 minutes to ≤20 minutes; d, >20 minutes; z, epinephrine not administered						
The final grade of the reaction will not be determined until the event is over, regardless of the medication administered. The final report should include the first						
symptom(s)/sign(s) and the time of onset after the subcutaneous allergen immunotherapy injection iii and a suffix reflecting if and when epinephrine was or was not administered, e.g., Grade 2a; rhinitis: 10 minutes.						
Final Report: Grade a-d, or z	First symptom	Time of onset of first symptom				
Comments iv						

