**16.3. LABORATORY EVALUATIONS**

Results from the central laboratory are to be included in the reporting of this study for Haematology, Biochemistry, Urine dipstick and Immunology. Quantitative laboratory assessments are to be summarised by descriptive statistics and presented in International System of Units (SI). Categorical assessments are to be presented by frequency (n) and percentage (%) of subjects.

---

Document: TH005 SAP Version 2.docx

Author: [name]

Version Number:

2.0

Version Date:

24MAR2017

Template No: CS\_TP\_BS016 – Revision 3

Effective Date: 01May2012

Reference: CS\_WI\_BS005

Copyright © 2012 Quintiles Transnational Corp. All rights reserved.

The contents of this document are confidential and proprietary to Quintiles Transnational Corp. Unauthorized use, disclosure or reproduction is strictly prohibited.

---

Quantitative laboratory assessments reported as “< X”, i.e. below the lower limit of quantification (BLQ), or “> X”, i.e. above the upper limit of quantification (ULQ), are to be converted to X for the purpose of quantitative summaries, but are to be presented as recorded, i.e. as “< X” or “> X” in the listings.

The following summaries are to be provided for laboratory data:

- Actual and change from Baseline by visit (for quantitative measurements)
- Shift from Baseline according to normal reference range criteria (for quantitative measurements and categorical measurements) by visit
- Listings of all laboratory assessments

The following assessments are to be measured and presented:

- Haematology: Haematocrit, haemoglobin, red blood cells, white blood cells (WBC), WBC differentials (neutrophils, eosinophils, basophils, lymphocytes, monocytes) and platelets
- Biochemistry: Sodium, potassium, chloride, urea, creatinine, calcium, phosphorus, total protein, albumin, uric acid, total bilirubin, glucose (random), lactate dehydrogenase, creatine phosphokinase, alanine transaminase, aspartate transaminase, gamma glutamyltransferase and alkaline phosphatase
- Urine dipstick: pH, protein, ketones, blood and glucose
- Immunology: All relevant perennial allergen specific IgE
- Tryptase for anaphylactic response

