### **16.7. OTHER SAFETY ASSESSMENTS**

#### **16.7.1. FORCED EXPIRATORY VOLUME IN 1 SECOND (FEV1)**

The FEV1 is to be measured at Screening, prior to and 30 minutes post study medication administration (Visits

---

Document: TH005 SAP Version 2.docx  
Author: [name]

Version Number: 2.0  
Version Date: 24MAR2017

Template No: CS\_TP\_BS016 – Revision 3  
Effective Date: 01May2012

Reference: CS\_WI\_BS005

Copyright © 2012 Quintiles Transnational Corp. All rights reserved.  
The contents of this document are confidential and proprietary to Quintiles Transnational Corp. Unauthorized use, disclosure or reproduction is strictly prohibited.

3A-3H), at the End of Dosing Assessment (Visit 3I), and at the end of the PAC1 (Visit 4B), PAC2 (Visit 4D) and PAC3 (Visit 4F) periods.

At each assessment  $FEV_1$  is to be measured according to the American Thoracic Society guidelines with the subject sitting and the highest reading is to be recorded in the eCRF.

Absolute and change from Baseline/pre-dose values of  $FEV_1$  is to be summarised by descriptive statistics and treatment group for each visit.

- For medication administration visits (Visit 3A to Visit 3H), change from pre-dose to 30 minutes post-dose observation is to be presented
- For all other visit assessments (including the pre-dose assessment at Visit 3A to Visit 3H), change from Baseline is to be presented
- $FEV_1$  data is to be listed
- An additional listing is to be created for any reduction in  $FEV_1$  of more than 20% from Baseline/pre-dose, as well as a reduction of more than 30% from Baseline/pre-dose
  - The frequency (n) and percentage (%) of subjects with a reduction of more than 20% from Baseline/pre-dose as well as a reduction of more than 30% from Baseline/pre-dose is to be presented by treatment group at each applicable visit.  
Percentages are to be calculated relative to the total number of subjects in the analysis population with data available.

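### SAP 6.3 keeps unscheduled and repeat readings out of the by-visit FEV1 threshold counts, laboratory shifts and vital-sign summaries, and no worst-value table makes up for it

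*SAP*

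**What the plan says.** SAP 6.3 sets three rules for safety data.

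- Unscheduled readings: "Unscheduled measurements are not to be included in by-visit summaries, but may contribute to the Baseline value".
- Retests at a post-baseline visit: "the first measurement (original value) for that visit is to be used for by-visit summaries".
- Listings: "Listings are to include scheduled, unscheduled, retest and early discontinuation data".

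The tables that these rules govern are organised by visit. In SAP 16.7.1, the number and percentage of subjects with an FEV1 fall above 20%, and above 30%, "is to be presented by treatment group at each applicable visit". SAP 16.3 plans laboratory values and changes by visit and, as its categorical summary, "Shift from Baseline according to normal reference range criteria (for quantitative measurements and categorical measurements) by visit". SAP 16.5 gives descriptive statistics for vital signs at each visit and no threshold counts. SAP 16.7.1 also requires a separate listing of FEV1 falls beyond the same two thresholds.

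The protocol expects some readings outside the schedule. On laboratory work, Protocol 6.4.4.4 says: "Additional tests may be performed if clinically warranted".

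**The concern.** Leaving unscheduled readings out of by-visit means is sound, because it stops subjects who were measured more often from distorting the mean at a visit. A count of subjects who crossed a threshold, or a shift to an abnormal category, asks something different: did this subject ever have such a value on treatment? Readings taken because a subject is unwell are the ones most likely to answer yes, and the rule removes them.

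The schedule is sparse enough for this to matter. FEV1 and vital signs have one scheduled post-dose reading, at 30 minutes, and Protocol 6.2.2.1 lets subjects leave from 30 minutes onward. Once dosing has started, haematology, biochemistry and dipstick tests are scheduled only at Visit 3I (week 32) and Visit 5 (week 52).

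The protocol itself records open safety questions. Section 1.3.1 gives 12 nmol as the highest unit dose studied so far, while one arm receives 20 nmol. Section 1.2 notes that neither completed study enrolled subjects with asthma, although a tolerability study in asthmatics was under way.

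**Working it through.** The plan states no figure to reproduce, so the check traces each type of measurement from schedule to output.

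| Data | Scheduled after first dose | Planned summary | Does an off-schedule or repeat value enter it? | Where else it appears |
|---|---|---|---|---|
| FEV1 | 30 min after each of 8 doses, before doses 2 to 8, Visit 3I, end of each PAC period | By-visit statistics; by-visit counts above 20% and 30% | No | Listing of falls beyond the thresholds; AE or AESI if reported |
| Vital signs | Same dosing-day times, Visit 3I, PAC visits, Visit 5 | By-visit statistics only | No | Listing; AE if reported |
| Haematology, biochemistry, dipstick | Visits 3I and 5 | By-visit values and shifts | No | Listing; AE if clinically significant |
| AEs | Not tied to a schedule | Treatment-emergent AE (TEAE) counts by subject and mention | Yes | – |

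**Step 1: one subject followed through SAP 16.7.1.** Suppose the 30-minute FEV1 shows a fall below 20%, and a reading at 45 minutes shows a 40% fall. Protocol 6.2.2.1 allows ±5 minutes around the nominal time, so the later reading is not the scheduled one. If it is recorded as unscheduled, the first rule excludes it. If it is recorded under the same visit number, it meets the SAP's definition of a retest, and the first-value rule excludes it. Either way the subject is in the listing and absent from both threshold counts. The section can therefore give two different answers for the same arm.

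**Step 2: the missing any-time count.** The FEV1 counts are made separately at each visit. A subject who crosses the threshold at two dosing visits appears in two rows, so the rows cannot be added to give the number of subjects who ever crossed it. That number is not planned, even for scheduled readings.

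**Step 3: laboratory shifts.** A test drawn between scheduled visits because it was clinically indicated belongs to neither Visit 3I nor Visit 5. If the value has returned to normal by the next scheduled sample, the shift table shows no shift.

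**Step 4: vital signs.** There is no threshold count to be too low. The effect is that the minimum and maximum in the by-visit statistics (SAP 6.6) omit off-schedule extremes.

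**Step 5: size per subject.** The FEV1 denominator is subjects with data, at most about 165 per arm. Each subject missed lowers the percentage by 1/165 = 0.6 percentage points. The number missed cannot be derived from the documents. It is zero if every extreme value falls on a scheduled reading.

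**The case against.** The strongest reply is that clinically important events are already counted by another route. Systemic allergic reactions, whose grading in Protocol Appendix 4 refers to the size of the FEV1 drop, are AESIs reported like serious AEs (Protocol 6.4.2.1). A laboratory value judged clinically significant has to be recorded as an AE, and a one-grade CTCAE rise should ordinarily be reported (6.4.4.4). SAP 16.1 counts TEAEs, AESIs and events within 24 hours of any dose, by subject and by mention, with no restriction to scheduled visits. Protocol 7.5.4 makes AE counts the primary safety endpoint. All of this stands. A reader might infer from SAP 6.3 that readings taken during a reaction never reach any planned safety count; the documents do not support that. The subject in Step 1 would be counted as an AESI if the event was reported as a systemic reaction.

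The AE route does not replace the measurement tables, however. SAP 16.1 presents incidence by system organ class and preferred term, and specifies no table by reaction grade or size of FEV1 fall. Reporting rests partly on the investigator's judgement, and SAP 16.3.1 puts the investigator's assessment of laboratory significance in listings only. A numeric fall that is not reported as an AE is therefore never tabulated.

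Four smaller points:

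- The dedicated FEV1 listing is a real safeguard, since a reviewer can find the subjects there. It gives no by-arm percentages.
- SAP 6.3 introduces its by-visit rule as a general one, so exceptions are possible. Sections 16.3, 16.5 and 16.7.1 make none.
- Letting unscheduled values set Baseline may look one-sided, but the rule is the same in every arm. For FEV1 and vital signs the scheduled pre-dose reading at Visit 3A will usually be the last value before treatment, so it matters little there.
- The table templates and the DSMC SAP are separate documents and were not available. They may contain worst-value outputs.

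**Conclusion.** The point holds as a gap in the measurement tables. Under the SAP as written, extremes of FEV1, laboratory values and vital signs obtained off schedule or on repeat appear only in listings and, if reported, as AEs or AESIs. By-arm FEV1 threshold counts and laboratory shifts can be too low, never too high, relative to all data collected. The FEV1 count can also contradict the listing beside it.

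The primary safety endpoint and the TEAE and AESI counts are not affected, and no inferential safety test depends on these tables. No overall size can be given, because the frequency of unscheduled and repeat readings is not stated. The gap also concerns only values that were actually measured. An abnormality that came and went with no sample drawn is a consequence of the visit schedule, not of SAP 6.3.

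The conclusion assumes that the unseen templates follow the SAP text. It is a worthwhile, inexpensive improvement to the safety tables.

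**What to change.** Keep SAP 6.3 unchanged for by-visit means and add the following, each using all post-baseline values including unscheduled and repeat measurements.

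- **16.7.1 (FEV1).** Count each subject once in each of two summaries: the worst value after each dose, up to the next dosing visit (or Visit 3I after the last dose), relative to that visit's pre-dose reading; and the worst post-baseline value overall. For each, give the number and percentage of subjects by arm with a fall above 20% and above 30%. The overall count should agree with the listing.
- **16.3 (laboratory).** Shift from Baseline to the worst post-baseline category, one entry per subject and test, with low and high shown separately.
- **16.5 (vital signs).** Worst post-baseline change per subject, with largest rise and largest fall shown separately.
- **6.3.** A sentence stating that these summaries are exempt from the exclusion and from the first-value rule.

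The cost is SAP wording and a few table rows, since the data are already collected and listed. The safety percentages will look slightly less favourable. A worst-value summary also rises with the number of readings taken and can pick up a poor spirometry effort or a laboratory error, so it should stand beside the by-visit tables and not replace them. No study procedure or efficacy analysis changes.

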#### Pre-dose assessments:

- Recording of any AEs.
- Recording of any changes to concomitant medication since last visit.
- Urine pregnancy test (for females and which must be negative for the subject to continue in the study).
- Examination of the injection site from previous administration (not relevant for Visit 3A) with recording of any injection site reaction on the following scale (FDA Guidance for Industry 2007) (Table 7):

	Grade 0	Grade 1	Grade 2	Grade 3	Grade 4
Pain	None	Does not interfere with activity	Repeated use of non-narcotic pain reliever >24 hours or interferes with activity	Any use of narcotic pain reliever or prevents daily activity	Emergency room visit or hospitalization
Tenderness	None	Mild discomfort to touch	Discomfort with movement	Significant discomfort at rest	Emergency room visit or hospitalization
Erythema/ Redness *	None	2.5 – 5 cm	5.1 – 10 cm	>10 cm	Necrosis or exfoliative dermatitis
Induration/ Swelling**	None	2.5 – 5 cm and does not interfere with activity	5.1 – 10 cm or interferes with activity	>10 cm or prevents daily activity	Necrosis

**Table 7** Grading of Injection Site Reactions

- Spirometry (FEV1) [asthmatic subjects should not take their  $\beta$  agonist asthma medication for a minimum of 4 hours prior to spirometry]. FEV1 must be  $\geq$ 70% of predicted for a subject to be dosed.
- In the event that the FEV1 is less than 70% of predicted the subject's asthma medication use should be reviewed and any appropriate adjustments made. The dosing visit should then be rescheduled within 5 days. A dosing visit may only be rescheduled once, after which time it becomes a missed visit.
- Vital signs (seated or semi-recumbent).
- Blood sample for biomarker analysis (OPTIONAL sub-study ONLY at Visit 3A see Section 6.4.4.7)

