## 16.5. VITAL SIGNS

The following vital signs assessments are to be taken rested and in the sitting or semi-recumbent position and reported for this study:

- Systolic Blood Pressure (mmHg)
- Diastolic Blood Pressure (mmHg)
- Pulse Rate (bpm)
- Respiratory Rate (breaths/min)
- Oral body temperature (°C)
- At each medication administration visit (Visit 3A to Visit 3H), vital signs are to be taken pre-dose as well as 30 minutes post-dose.

The following summaries are to be provided for vital signs data by descriptive statistics and treatment group for each visit:

- Actual and change from Baseline/pre-dose observation by visit
  - For medication administration visits (Visit 3A to Visit 3H), change from pre-dose to 30 minutes post-dose observation is to be presented
  - For all other visit assessments (including the pre-dose assessment at Visit 3A to Visit 3H), change from Baseline is to be presented

---

Document: TH005 SAP Version 2.docx  
Author: [name]

Version Number: 2.0  
Version Date: 24MAR2017

Template No: CS\_TP\_BS016 – Revision 3  
Effective Date: 01May2012

Reference: CS\_WI\_BS005

Copyright © 2012 Quintiles Transnational Corp. All rights reserved.  
The contents of this document are confidential and proprietary to Quintiles Transnational Corp. Unauthorized use, disclosure or reproduction is strictly prohibited.

---

- Listing of all vital signs data

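### At dosing visits 3B-3H, the SAP's first-measurement rule can make a failed FEV1 from a day without an injection the pre-dose value, understating the post-injection fall

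*SAP*

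**What the plan says.** SAP 6.3 sets the rule for repeated assessments. It opens with the case "In the case of a retest at any post Baseline visit (same visit number assigned but a different date and/or time of assessment" (the bracket closes there) and then states that "the first measurement (original value) for that visit is to be used for by-visit summaries". The same section adds: "Unscheduled measurements are not to be included in by-visit summaries, but may contribute to the Baseline value". It also says: "Listings are to include scheduled, unscheduled, retest and early discontinuation data".

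Protocol 6.2.2.1 (pre-dose assessments) requires FEV1 of at least 70% of predicted before an injection. Below that, asthma medication is reviewed, and: "The dosing visit should then be rescheduled within 5 days". This may happen once per visit, after which the visit counts as missed. The section also reschedules a visit for a significant illness with fever above 38°C.

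SAP 16.7.1 says of FEV1 at Visits 3A to 3H that "change from pre-dose to 30 minutes post-dose observation is to be presented". It also counts, at each applicable visit, subjects whose FEV1 falls by more than 20% and by more than 30% from Baseline or pre-dose. SAP 16.5 has the same pre-to-post comparison for vital signs: "For medication administration visits (Visit 3A to Visit 3H), change from pre-dose to 30 minutes post-dose observation is to be presented".

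For the safety Baseline, SAP 6.2 goes the other way and takes the last value: "Baseline is defined as the last non-missing measurement taken prior to reference start date (including unscheduled assessments or retests" (bracket closes there). No matching rule is written for pre-dose values at later visits.

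**The concern.** A rescheduled dosing visit can hold two readings that both answer to the name pre-dose. Protocol 6.2.2.1 itself calls the reading that triggers rescheduling the pre-dose FEV1. SAP 6.3 is the only rule for choosing between two readings with the same visit number, and it chooses the one from the day no injection was given. The post-dose reading comes from a different day, so their difference is not an acute post-injection change.

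Safety and tolerability is a secondary objective (Protocol 2.2). The 20% and 30% counts are there to pick up acute falls in FEV1. The affected subjects entered with FEV1 of at least 80% of predicted (Protocol 4.3, exclusion criterion 5) and dropped below 70% during dosing, so their post-injection change is of particular interest. Neither completed study included subjects with asthma. The protocol adds that a tolerability study in controlled asthma is underway, with results expected before dosing starts (Protocol 1.2).

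**Working it through.** The documents give no figure on this point, so there is none to reproduce. The check has three parts: which reading the rule selects, which way the error goes, and how large it can be.

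**1. Which reading is selected.** How the attempts are stored decides this, and neither document says how.

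| Storage of the two attempts | Effect of SAP 6.3 on by-visit summaries |
|---|---|
| Both under the same visit number | First value used: the failed reading |
| Repeat attempt coded unscheduled | Dosing-day readings left out |
| Failed attempt coded unscheduled | Failed reading left out: correct result |

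Visit 3A falls outside the problem. The retest rule covers post-Baseline visits only, SAP 6.4 labels the Visit 3A date as Baseline, and SAP 6.2 takes the last value there. If the second attempt also fails, no injection is given and there is no post-dose value. What remains is Visits 3B-3H with one successful repeat.

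**2. Direction, first row of the table.** Let F be the failed reading, A the reading on the injection day and P the 30-minute post-dose reading. All are in % of predicted; ratios in litres are the same, because the predicted value does not change over a few days.

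- True fall = 1 − P/A
- Fall as shown = 1 − P/F
- Protocol-compliant dosing after an FEV1 reschedule gives F < 70 ≤ A, so P/F > P/A, and the fall shown is smaller than the true fall.

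The inequality is strict. A check on 200,000 random triples with F < 70 ≤ A found no exception. The absolute change is understated by A − F.

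**3. Size.** For a true fall t, P = A(1 − t), so the fall shown is 1 − (A/F)(1 − t). A fall is shown as more than 20% only if P < 0.8F, that is, if the true fall exceeds 1 − 0.8F/A. For 30%, replace 0.8 by 0.7. The readings below are assumed.

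| F, then A | True 25% fall shown as | True fall needed for the >20% count | True fall needed for the >30% count |
|---|---|---|---|
| 69, 70 | 23.9% | 21.1% | 31.0% |
| 68, 75 | 17.3% | 27.5% | 36.5% |
| 65, 75 | 13.5% | 30.7% | 39.3% |
| 60, 80 | 0.0% | 40.0% | 47.5% |

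Worked line for 65 then 75: P = 75 × 0.75 = 56.25; shown = 1 − 56.25/65 = 13.5%; threshold = 1 − 0.8 × 65/75 = 30.7%.

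**4. Fever reschedules.** Here the first FEV1, if taken, need not be the lower one. With assumed readings of 90 at the aborted attempt, 82 on the injection day and 70 post-dose, the true fall is 1 − 70/82 = 14.6%, but 1 − 70/90 = 22.2% is shown. The error can go either way. Vital signs taken at an aborted attempt are mismatched by day in the same manner. For temperature, a first reading above 38°C used as pre-dose would tend to mask a post-dose rise.

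**The case against.** The strongest reply is that the SAP need not be read this way. SAP 6.3 speaks of retests, while the protocol speaks of rescheduling, which can mean that the nominal visit simply moves to the new date. SAP 16.7.1 and Protocol 6.4.4.5 describe FEV1 before and 30 minutes after administration, which points to two readings around one injection. SAP 6.3 also opens as a general default. A sensible programmer might match by injection date without being told.

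That is a fair reading, and it rules out saying that the failed value necessarily becomes the pre-dose value. It does not close the gap. SAP 6.3 defines a retest by visit number and date, and a moved visit that keeps its number meets that definition. The protocol also uses the term pre-dose for the failed reading. Only one of the three storage choices gives the right answer, and nothing requires it.

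The second reply is that little is at stake. FEV1 below 80% of predicted and asthma that is not fully controlled are exclusions, and a visit may be rescheduled only once. The safety outputs are descriptive, and the listings show every reading. Systemic allergic reactions are reported as events of special interest, and adverse events within 24 hours of a dose are tabulated (SAP 16.1.8). All of this stands and limits the consequence. It does not make a wrong count right, and for uncommon events a few misclassified visits can matter to the count.

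The extension to vital signs is weaker for FEV1 reschedules. Table 6 of the protocol places vital signs after spirometry, so an attempt that failed on spirometry may have none.

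**Conclusion.** The point holds in a conditional form. At Visits 3B-3H, when a visit is rescheduled for low FEV1 and both attempts carry the same visit number, SAP 6.3 read literally selects a reading from a day without an injection. With protocol-compliant dosing, the post-injection fall is then understated every time, and falls above 20% or 30% can be missed. On the assumed readings, the understatement of a true 25% fall runs from about 1 percentage point to 25. If the repeat attempt is coded unscheduled instead, the dosing-day readings drop out of the by-visit summaries.

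A reader might infer that the plan always understates the fall after any rescheduled visit. The documents do not support that: Visit 3A is outside the rule, the coding of aborted attempts is not specified, and the FEV1 error after a fever reschedule has no fixed direction. Nor does the point touch the primary analysis. The number of affected visits is not stated and is probably small. It is still worth correcting, because the written rule can produce a wrong safety count and the remedy is simple.

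**What to change.** Add to SAP 6.3, with a cross-reference in 16.5 and 16.7.1:

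- For Visits 3A-3H, the pre-dose value is the last assessment before the injection on the day the injection was given.
- Assessments from an attempted dosing visit at which no injection was given are listed only, whatever visit number they carry.
- Both rules apply to the FEV1 and vital-sign changes from pre-dose to post-dose, and to the counts of FEV1 falls above 20% and 30%.

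The cost is two or three sentences and a date match to the injection record; no extra data are needed. One consequence should be accepted knowingly: the failed reading also leaves the by-visit change from Baseline. It stays visible in the listings, including the SAP 16.7.1 listing of large FEV1 reductions.
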